In iv studies in healthy subjects, modest and reversible alanine aminotransferase (ALT) increases were seen most notably with iv doses of 300 mg or greater (3 × higher than the therapeutic dose of 100 mg iv). There were no differences in ALT changes in the Phase 2 study compared to linezolid. Transient increases in heart rate were observed following administration of single and multiple doses of omadacycline, with a dose dependent mean increase of up to 15-20 beats per minute (bpm) compared to placebo for the first 4 hours after dosing. The increases in heart rate were not reported as AEs and not associated with any other cardiac findings. These increases were observed most consistently during the 2 hours immediately post-infusion. Beyond 6 hours after the start of the infusion, heart rate in all subjects, including controls, were comparable. A listing of all Phase 1 AEs is provided in Appendix I of the IB ([Paratek, 2014](#)).

In the Phase 2 study, omadacycline was well-tolerated. The most frequently reported AEs were GI-related occurring in 21 (18.9%) of 111 omadacycline-treated, and 18 (16.7%) of 108 linezolid-treated subjects. Nausea and vomiting were reported in 11 (9.9%) and 5 (4.5%), respectively, of omadacycline-treated subjects primarily during po treatment, compared to 8 (7.4%) and 4 (3.7%), respectively, of linezolid-treated subjects. Premature discontinuation of treatment due to an AE was very infrequent, occurring in 0.9% and 1.9% of omadacycline and linezolid-treated subjects, respectively.

There was no pattern of adverse changes in laboratory safety parameters among subjects treated with omadacycline or linezolid; changes in omadacycline-treated subjects were comparable to those observed with linezolid. In particular, there was no clinical or statistical difference between the treatment groups in ALT values or in other liver function tests (LFTs).

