12.2 Exclusion Criteria

1. Has received 1 or more dose(s) of a potentially effective systemic antibacterial treatment within the 72 hours prior to the first dose of test article (a subject will be considered to have received a potentially effective systemic antibacterial treatment if the pathogen identified as causing infection is shown to be susceptible to the antibacterial given or, in the circumstance

where a pathogen is not identified, if the antibacterial agent is approved for treatment of pneumonia or is known to have activity against any of the leading causes of CABP [eg, *Streptococcus pneumoniae*, *Haemophilus influenzae*, *Moraxella catarrhalis*, *Staphylococcus aureus*, *Legionella pneumophila*]). EXCEPTION: Subjects may be eligible despite prior antibacterial therapy if they have been treated with a single dose of a short-acting antibacterial (ie, an antibacterial whose standard dosing regimen is more frequent than once per day, see list in [Appendix 1](#)).

2. Is known or suspected to have CABP caused by a pathogen that may be resistant to either test article (eg, *Klebsiella pneumoniae*, *Pseudomonas aeruginosa*, *Pneumocystis jiroveci*, obligate anaerobes, mycobacteria, fungal pathogens).
3. Suspected or confirmed empyema (a parapneumonic pleural effusion is not an exclusion criteria) or lung abscess.
4. Subjects with known or suspected hospital-acquired pneumonia (HAP) or healthcare-associated pneumonia (HCAP). HAP is defined as pneumonia with onset of clinical signs and symptoms \geq 48 hours after hospitalization in an acute in-subject health care facility. HCAP is defined as pneumonia acquired in a long-term care or subacute/intermediate healthcare facility (eg, nursing home) or in a subject admitted with pneumonia following a recent hospitalization (discharged within 90 days of current admission and previously hospitalized for \geq 48 hours).
5. Has known or is clinically suspected to have 1 or more of the following prior to randomization:
 - ALT or aspartate aminotransferase (AST) \geq 2 \times Upper Limit of Normal (ULN),
 - total bilirubin $>$ 1.5 \times ULN, or
 - evidence of end-stage liver disease (eg, ascites, hepatic encephalopathy).
6. Has a known history of having experienced unstable cardiac disease (eg, unstable angina, myocardial infarction, acute congestive heart failure, unstable cardiac arrhythmia, etc.) within the 3 months prior to Screening.

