16.1.3 Laboratory Evaluations

Blood samples for hematology, chemistry and coagulation (prothrombin time only) should be drawn at Screening, Day 4, Day 7, Day 10, EOT, and PTE (see [STUDY FLOWCHART](#)). At Screening only, 1 sample will be analyzed at a local laboratory for confirmation of eligibility criteria and a second sample will be shipped to the Central Laboratory for analysis. At all other visits samples should be shipped to the Central Laboratory for analysis.

The Central Laboratory will be used for safety analysis of all specimens collected. Details on the collection tubes and containers, shipment of samples and reporting of results by the Central Laboratory are provided to investigators in the Central Laboratory Manual.

Because subject enrollment will not permit using Central Laboratory results to assess a subject's meeting inclusion/exclusion criteria, it is expected that local laboratory testing will be used in circumstances where this testing is needed to assess a subject's WBC count or differential, serum transaminase or bilirubin levels, serum creatinine or pregnancy testing (for women only).

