8.6 Visit Windows/Unscheduled Visits

For the primary efficacy outcome, if more than one complete assessment of the symptoms of CABP is done in the Early Clinical Assessment window of 72 to 120 hours after administration of the first dose of test article, the latest will be used. For secondary and additional efficacy outcomes, the data collected at the EOT and PTE Visits, regardless of when these occur will be utilized in the ITT and microITT analyses. The CE and ME populations exclude subjects with a visit occurring outside the window allowed per protocol.

For each safety outcome, analyses will utilize assessments occurring during the scheduled visit windows (provided in [Table 7](#)). Thus, if a subject has a visit outside the scheduled visit window, for example, a PTE Visit occurred 20 days after the subject's last day of therapy, the assessment will not be summarized with the PTE Visit but will be considered an unscheduled assessment. If a subject does not have an assessment at a scheduled visit and an unscheduled assessment was taken within the window for the time point (for example, 5 to 10 days after the subject's last day of therapy for PTE), these assessments will be summarized in the by time point analyses. If more than one measurement is taken during the visit window, the value taken on the scheduled visit will be utilized or if no scheduled visit was done, the first (earliest) measurement in the visit window will be used. If more than one measurement is taken on the same day, the assessment closest to the start of the dose will be used for on treatment values and the last measurement on the day will be used for post-treatment values. For worst overall post-baseline analyses, all assessments including those obtained from unscheduled visits will be included.

Table 7. Scheduled Study Visits

Study Visit	Study Day	Notes
Baseline	Day -1 or Day 1	Except where indicated, last measurement prior to the first dose of test article. Screening assessments are to be taken within 24 hours prior to the first dose of test article. If no test article is taken, the date and time of randomization is used in place of the first dose of test article.
On Treatment	Day 1-Day 10	Day 6 visit is optional for subjects that have been switched to po test article and have been discharged from a hospital setting. A Day 10 visit will be conducted for subjects with treatment extending beyond 9 days, unless this visit coincides with the EOT Visit.

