Clinically notable laboratory values will be determined based on the modified Division of Microbiology and Infectious Diseases (DMID) criteria in [Appendix 5](#). Shift tables will be presented to show the number of subjects with a laboratory value with a grade of 0, 1, 2, 3 or 4 at baseline versus the value at each visit and the worst post-baseline value. Number and percentage of subjects with at least a 2-grade increase from baseline (based on DMID criteria) will be summarized by treatment arm. Percentages for each laboratory test will be based on the number of subjects with a baseline and post-baseline evaluation of the specific laboratory test. A listing will be provided which gives all laboratory results for a given laboratory test for subjects who have at least one 2-grade increase from baseline.

The number and percentage (based on the number of subjects with a normal level at baseline) of subjects in each treatment group with an elevated transaminase level ($> 3 \times$ upper limit of normal [ULN], $> 5 \times$ ULN, and $> 10 \times$ ULN), an elevated bilirubin level ($> 1.5 \times$ ULN and $> 2 \times$ ULN) will be presented by study visit. A listing of subjects who meet the laboratory criteria for Hy's law at the same visit will also be provided. The laboratory criteria for Hy's law is defined as 1) ALT or AST $> 3 \times$ ULN, ALP $\leq 2.0 \times$ ULN, and total bilirubin > 1.5 ULN and 2) ALT or AST $> 3 \times$ ULN, ALP $\leq 2.0 \times$ ULN, and total bilirubin $> 2 \times$ ULN.

Detailed subject listings of all laboratory data collected during the study (local and central laboratory data) will be provided, including calculated creatinine clearance (using the Cockcroft-Gault equation). Laboratory values outside normal limits will be identified in the subject data listings with flags for low (L) and high (H) as will laboratory values that meet the clinically notable thresholds (CN).

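### The Hy's law listing in SAP 11.4 requires every criterion at one visit, so staggered transaminase and bilirubin peaks go unlisted; the liver threshold table lacks an any-post-baseline row and omits abnormal baselines

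*Combined protocol and SAP*

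**What the plan says.** SAP 11.4 defines two separate liver outputs.

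- **Threshold table.** It counts subjects with transaminases above 3, 5 and 10 × ULN and bilirubin above 1.5 and 2 × ULN. The percentages are "based on the number of subjects with a normal level at baseline", and the results "will be presented by study visit". No worst-value or any-time row is stated.
- **Hy's law listing.** The sentence ends "law at the same visit will also be provided". The criteria are ALT or AST > 3 × ULN, ALP ≤ 2 × ULN, and total bilirubin > 1.5 × ULN (first version) or > 2 × ULN (second version). The listing has no normal-baseline condition and does not say whether an unscheduled draw counts as a visit.

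Protocol v2.0 Section 16.1.3 says that blood samples "should be drawn at Screening, Day 4, Day 7, Day 10, EOT, and PTE". SAP 8.6 governs by-visit tables. If several measurements fall in a window, "the value taken on the scheduled visit will be utilized". An unscheduled value inside a window is used when the scheduled one is missing, and a value outside every window is not summarized by visit. Worst post-baseline analyses use everything, and SAP 11.4 adds that local and central results both count there.

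SAP 11.4 also plans shift tables of toxicity grade (Appendix 5) against each visit and the worst post-baseline value, a count and listing of subjects with at least a 2-grade increase, and full listings of all local and central results.

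**The concern.** The Hy's law listing is the only planned output that tests transaminases and bilirubin together in the same subject. It can be empty although a subject has crossed both limits, if the crossings were caught at different draws. The threshold table has a different weakness: it leaves out subjects who entered with a value above ULN, and it never gives a count over the whole post-baseline period.

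At stake is the hepatic safety summary. Protocol Section 9.1 names a liver signal, though a mild one: "modest and reversible alanine aminotransferase (ALT) increases were seen most notably with iv doses of 300 mg or greater". Elsewhere the SAP already reports on an any-time basis. Clinically notable vital signs get an overall post-baseline incidence that includes unscheduled visits (11.2), and QTcF increases are counted at any post-baseline time (11.3). No reason is given for the liver table to differ.

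**Working it through.** The plan states no figure to reproduce. The check sets the rules side by side and applies them to assumed cases.

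**1. Same-visit rule against the draw schedule.** Values are in multiples of ULN.

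- SAP rule: listed if, at some visit v, ALT or AST(v) > 3, ALP(v) ≤ 2 and bilirubin(v) > 1.5 (or > 2).
- Any-time rule for the two peaks: highest ALT or AST > 3, and highest bilirubin > 1.5 (or > 2), over all post-baseline draws.

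Meeting the first implies meeting the second, but not the reverse. Take a 7-day course with last dose on Day 7. The Day 10 visit applies only to treatment beyond 9 days. EOT falls on Days 7 to 9. PTE falls on Day 7 + 5 = 12 to Day 7 + 10 = 17. That gives Day 4, Day 7, EOT and PTE: four draws, or three if EOT coincides with Day 7. The EOT-to-PTE gap is 12 − 9 = 3 to 17 − 7 = 10 days. Nothing in the plan makes both peaks fall on one draw.

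**2. Who is outside the threshold table.** Exclusion 5 (Protocol 12.2) begins "Has known or is clinically suspected to have 1 or more of the following prior to randomization" and then names ALT/AST ≥ 2 × ULN and bilirubin > 1.5 × ULN. Subjects with ALT/AST above ULN but under 2 × ULN, or bilirubin above ULN up to 1.5 × ULN, can therefore enrol. They are not normal at baseline for that test.

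**3. What the Appendix 5 grades show.**

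- ALT/AST: grade 0 < 1.25; grade 1 = 1.25–2.5; grade 2 > 2.5–5; grade 3 > 5–10; grade 4 > 10.
- Bilirubin: grade 0 < 1.1; grade 1 = 1.1–1.5; grade 2 > 1.5–2.5; grade 3 > 2.5–5; grade 4 > 5.

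The worst-value shift tables therefore show ALT/AST > 5 and > 10 and bilirubin > 1.5. They do not show ALT/AST > 3 or bilirubin > 2, which both lie inside grade 2.

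For the 2-grade output:

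- Baseline ALT/AST 1.25 to under 2 is grade 1. A 2-grade rise means grade 3, so the peak must exceed 5; peaks above 3 and up to 5 are missed.
- Baseline ALT/AST above 1 and under 1.25 is grade 0. A peak above 2.5 qualifies.
- Baseline bilirubin 1.1 to 1.5 is grade 1. The peak must exceed 2.5; peaks above 2 and up to 2.5 are missed.

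**4. Assumed cases.** Values are hypothetical, ALP is 1 × ULN throughout, and normal baseline is judged test by test.

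| Case | Baseline ALT / bilirubin | Post-baseline | Threshold table | Hy's law listing | 2-grade output |
|---|---|---|---|---|---|
| A | 0.8 / 0.6 | Day 7: 4 / 2.2 | both tests | yes | both tests |
| B | 0.8 / 0.6 | Day 7: 4 / 0.9; PTE: 2.4 / 2.2 | both tests | **no** | both tests |
| C | 1.5 / 0.6 | Day 7: 4 / 2.2 | bilirubin only | yes | bilirubin only |
| D | 1.5 / 0.6 | Day 7: 4 / 0.9 | no | not applicable | no |
| E | 0.8 / 0.6 | unscheduled, outside windows: 4 / 2.2 | no | yes, as worded | both tests |
| F | 1.5 / 1.2 | Day 7: 4 / 1.2; PTE: 2.4 / 2.2 | no | **no** | no |

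B and F meet the any-time rule but are unlisted. B's two elevations appear in separate tables, unlinked. F appears only as two unlinked grade 1 to 2 shifts and in the raw listings.

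**The case against.** A reader might infer that the normal-baseline restriction removes Hy's law cases. It does not: that restriction belongs to the threshold table, and case C is listed. A reader might also infer that the Hy's law listing ignores unscheduled draws. The text does not say so; as worded, case E is listed. Even the by-visit table takes an in-window unscheduled value when the scheduled one is missing.

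The planned grade outputs also do real work. Any subject with baseline ALT/AST under 2 × ULN who later exceeds 5 × ULN rises at least 2 grades and enters both the count and the listing, so severe elevations in abnormal-baseline subjects are not lost. Every result is listed, and the DSMC reviews laboratory data about quarterly.

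The background is also reassuring. Section 9.1 reports no ALT difference from linezolid in Phase 2, and ALT-related adverse events in 1.5% on omadacycline against 5.6% on linezolid in the terminated Phase 3 study.

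All of this stands, and it narrows the point. It does not answer the same-visit rule, because none of these outputs screens for the two tests together. A full data listing holds the values but does not select the subjects.

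**Conclusion.** The point holds in two limited parts.

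First, the same-visit condition keeps subjects with non-concurrent peaks off the only output that combines transaminases and bilirubin. This follows from the wording alone.

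Second, the threshold table has no any-post-baseline count and no abnormal-baseline group. The grade outputs only partly make up for this: the uncovered range for ALT/AST is baseline 1.25 to under 2 × ULN with a peak above 3 and up to 5 × ULN. That bound assumes the analysis baseline respects Exclusion 5. Eligibility uses local results and the analysis baseline is central, so higher baselines are possible; up to 2.5 × ULN the grade is still 1 and the bound of 5 × ULN is unchanged.

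No count can be attached to either part. The documents do not give the share of subjects with abnormal liver tests at entry, or how often the peaks would be staggered. Nor do they support saying that cases will be missed, only that the listing as written would not show them. Efficacy analyses, alpha and sample size are unaffected. This is an inexpensive improvement to safety reporting.

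**What to change.** Amend SAP 11.4 as follows.

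1. Add a listing of subjects who meet the ALT/AST criterion and the bilirubin criterion (> 1.5 and > 2 × ULN) at any post-baseline time, not necessarily together, using all central, local and unscheduled values. Flag same-visit cases as a subset, say whether an unscheduled draw counts as a visit, and state the draw at which the ALP condition is read.
2. Add to the threshold table an any-post-baseline row using all values, for all Safety subjects with a post-baseline value, split by baseline ≤ ULN and > ULN. The by-visit rows can stay.

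The cost is SAP wording and the programming of one table and one listing, from data already collected. The downside is that a few more subjects will be listed and need review for an alternative cause.

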11.5 Physical Examinations

Subject listings of all physical examination results by body system will be provided. Physical examination results will be coded using MedDRA Version 17.1. Any changes from baseline will be recorded as adverse events.

12 RESOURCE UTILIZATION ANALYSES

Descriptive statistics of the following resource utilization parameters will be provided by treatment group:

- Number of days in the hospital from the time of initiation of test article until discharge. Analyses will be completed only for those subjects admitted to the hospital and separately for all subjects. For the latter, subjects who are not admitted to the hospital will be assigned a value of 0 for number of days in the hospital. Analyses will also be completed by country.
- Number of days in the hospital from the time of initiation of rescue antibiotic (ie, a second antibiotic) therapy until discharge. Analyses will be completed only for those subjects admitted to the hospital and who required a second antibiotic therapy (ie, were treatment failures) and separately for all subjects. For the latter, subjects who are not admitted to the hospital or who did not require a second antibiotic therapy will be assigned a value of 0 for number of days in the hospital. Analyses will also be completed by country.
- Number of days in the hospital from the time of admission for CABP until discharge. Analyses will be completed only for those subjects admitted to the hospital and separately for all subjects. For the latter, subjects who are not admitted to the hospital will be assigned a value of 0 for number of days in the hospital. Analyses will also be completed by country.
- Duration (days) of test article.
- Other test article exposure variables are described in [Section 9.3](#).

13 OTHER RELEVANT DATA ANALYSES/SUMMARIES

13.1 Protocol Deviations

A listing of all protocol deviations will be provided. Deviations will also be reviewed by the Sponsor and categorized into general categories such as: randomization, at least one inclusion criterion not met, at least one exclusion criteria met, study procedures/visits not done, study visit outside window, noncompliance with dose, and use of prohibited medications or treatments, consent-IRB compliance issues, etc. The Sponsor will also categorize the protocol deviations as major and minor. Review of protocol deviations will be conducted and finalized prior to unblinding the database. The number of subjects with at least one protocol deviation, the number of subjects with a minor protocol deviation, the number of subjects with a major protocol deviation, and the number of subjects with at least one major deviation in each category will be presented by treatment group for the ITT population. A major deviation is defined as one that potentially affects the efficacy and/or safety analyses.

13.2 Prior and Concomitant Medications

All medications taken within 7 days prior to the date of informed consent through the Final Follow-up Visit will be recorded on the eCRF. Prior medications will be summarized by WHODRUG (Version 01 Dec 2014) Anatomical Therapeutic Chemical Classification (ATC) level 3 (third level indicates the therapeutic/pharmacologic subgroup) and generic medication name. Medications are considered prior if taken prior to the first infusion of test article or if their start date is unknown. Subjects will be counted only once for an ATC class and generic medication name. Concomitant medications taken during and after the study treatment period will be similarly summarized. Medications are considered concomitant if taken on or after the first infusion of test article, or if their stop date is unknown or marked as continuing.

The number and percentage of subjects who receive the following prior and concomitant medications will be summarized by treatment group:

- Systemic antibacterial medications taken within 72 hours prior to first infusion of test article and the reasons for receipt (ITT and CE-PTE populations)
- Systemic antibacterial medications (excluding test article) taken between first infusion of test article and the EOT Visit (CE-EOT population) and the reasons for receipt
- Systemic antibacterial medications (excluding test article) taken between first infusion of test article and the PTE Visit (CE-PTE population) and the reasons for receipt
- Non-antibacterial medications taken prior to informed consent through the first infusion of test article (ITT and Safety populations)
- Non-antibacterial medications taken from the first infusion of test article through the Final Follow-up Visit (ITT and Safety populations)

Appendix 1 Schedule of Assessments and Procedures

Study Phase		Double-Blind Phase										Follow-up Phase	
		iv Treatment Phase				iv or po Treatment Phase							
Study Day ^a	Screening ^b	Day 1		Day 2	Day 3	Day 4	Day 5	Day 6 ^c	Day 7	Day 10 ^e	EOT ^d	PTE ^e	Final Follow-up ^f
		iv dose 1	iv dose 2										
Screening and Eligibility Procedures													
Signed Informed Consent ^g	X												
Medical History, current medical conditions, demography	X												
Assessment of CABP symptom severity ^h	X			X	X	X	X	X	X	X	X		
Chest X-ray or CT scan ⁱ	X												
PORT Risk Class, ABG ^j	X												
Blood and urine samples for local lab hematology/chemistry/urinalysis/pregnancy ^k	X												
Review of Inclusion and Exclusion criteria/Randomization (if Eligible)	X												
Clinical Procedures and Test Article Administration													
Test Article Administration and Accountability ^l		X	X	X	X	X	X	X	X	X	X		
Physical examination ^m	X			X	X	X	X	X	X	X	X	X	
Vital signs	X	X ⁿ	X ⁿ	X ⁿ	X	X	X	X	X	X	X	X	
12-lead ECG ^o	X	X		X					X		X		
Blood for Central Lab tests: hematology/chemistry/pregnancy	X ^p					X			X	X	X ^p	X ^p	
Adverse Events ^q	X	X-----											X
Prior & Concomitant Medications ^r	X	X-----											X
Plasma samples (in heparin) for PK analyses ^s				X	X	X	X						
Assessment for po Switch or need for continued therapy ^t						X	X	X	X	X			

Study Phase		Double-Blind Phase										Follow-up Phase			
		iv Treatment Phase				iv or po Treatment Phase									
Study Day ^a	Screening ^b	Day 1		Day 2	Day 3	Day 4	Day 5	Day 6 ^c	Day 7	Day 10 ^c	EOT ^d	PTE ^e	Final Follow-up ^f		
Investigator's Assessment of Clinical Response												X	X		
Microbiological Procedures															
Blood culture ^u	X	As Clinically Indicated													
Respiratory culture & Gram stain ^v	X											X			
Urine for Local lab Legionella pneumophila and Streptococcus pneumoniae antigen test	X												X		
Blood for Central lab Legionella pneumophila , Mycoplasma pneumoniae & Chlamydophila pneumoniae serology	X												X		

ABG = arterial blood gas; AE = adverse event; BP = blood pressure; β -hCG = beta – human Chorionic Gonadotropin; CABP = community-acquired bacterial pneumonia; CT = computed tomography; CXR = chest X-ray; ECG = electrocardiogram; eCRF = electronic case report form; EOT = end of treatment; ICF = informed consent form; IxRS = Interactive Voice Response System/Interactive Web Response System; PK = pharmacokinetics; PTE = post-therapy evaluation; SAE = serious adverse event.

- ^a Study Day 1 is the first day of test article administration. Subsequent study days may be consecutive calendar days.
- ^b Following the signing of an ICF, all Screening evaluations should be completed within the 24 hours prior to the first dose of test article.
- ^c The Day 6 visit is optional for subjects that have been switched to po test article and have been discharged from a hospital setting. A Day 10 visit should be conducted for subjects with treatment extending beyond 9 days, unless this visit coincides with the EOT visit.
- ^d To be conducted on the day of, or within 2 days following the last dose of test article. Should also be conducted for any prematurely withdrawn subject.
- ^e To be conducted 5 to 10 days after the subject's last day of therapy.
- ^f To be conducted 30 to 37 days after the start of the first infusion of test article. The Final Follow-up assessment may be conducted via telephone contact or by another interactive technology for subjects who were considered to be Clinical Successes and had no AEs noted at or after the PTE visit. Otherwise, the visit must be conducted in person.
- ^g Written and signed ICF must be obtained before any assessment is performed.
- ^h The investigator should assess the severity of the subject's CABP symptoms of cough, sputum production, pleuritic chest pain, and dyspnea based upon the Community- Acquired Bacterial Pneumonia Subject Symptom Severity Guidance Framework for Investigator Assessment in [Appendix 3](#) of the protocol.
- ⁱ Subjects must have a confirming CXR or CT scan consistent with acute bacterial pneumonia within the 24 hours prior to the first dose of test article.
- ^j Only subjects with a PORT Risk Class of II, III or IV are eligible for enrollment, see [Appendix 2](#) of the protocol.
- ^k Local laboratory hematology and chemistry evaluations required for assessing subject eligibility, urinalysis for WBC, a urine pregnancy test (for women only), serum transaminase or bilirubin levels.

- ¹ The total duration of test article therapy (iv plus po) for all subjects will be at least 7 days and no more than 14 days. The pharmacist or designee will be unblinded to prepare appropriate doses of the IxRS identified test article. An unblinded monitor will perform drug accountability and review the pharmacist's records. Subjects discharged with po test article will be asked to return all unused test article and packaging at each visit (see [Section 24](#) of the protocol). At the EOT visit subjects discharged with po test article will return any remaining unused po test article and site staff will perform accountability.
- ^m A full physical examination will be completed at Screening (see [Section 14.2.2](#) of the protocol), thereafter only changes from Screening measurements should be recorded as AEs in the eCRFs.
- ⁿ For the first 3 doses of test article heart rate and BP should be recorded at the following times: just prior to the first infusion, within 30-90 minutes after the start of the first infusion, and at 3.5-5.5 hours after the start of the first infusion (see [Table 1](#) and [Section 16.1.2](#) of the protocol).
- ^o A 12-lead ECG should be performed just prior (within 30 minutes) and 30-90 minutes after the start of the first infusion of the first and third doses of test article, at the Day 7 visit, at the EOT visit, and as otherwise clinically indicated (see [Section 16.1.4.1](#) of the protocol).
- ^p Blood will be collected from all female subjects for a serum β-hCG pregnancy test at the Central Laboratory at the Screening, EOT and PTE visits.
- ^q A subject's AEs and SAEs will be recorded and reported from signing of the ICF to the Final Follow-up assessment.
- ^r Treatments that have been administered within the 7 days prior to the date of signing the ICF or during the Screening phase will be recorded in the eCRF. All medications and significant non-drug therapies administered after the first dose of test article must be recorded in the eCRF (see [Section 13](#) of the protocol).
- ^s Up to 4 samples will be collected per subject. The PK sample collection schedule for the individual subject will be provided by the sponsor (see [Section 19](#) of the protocol).
- ^t At any time after the first 3 days of iv treatment (after 4 iv doses) the subject may be switched to po medication based upon determination of clinical stability. Refer to protocol [Section 14.3.1.2](#) of the protocol for required criteria to switch to po treatment. At the investigator's discretion, all therapy may be discontinued after the seventh day of treatment (after 8 iv or po total doses), when the infection is considered clinically cured (based on normalization of the clinical signs and symptoms of infection and the investigator's clinical assessment that continued systemic antibacterial therapy is no longer needed).
- ^u If Screening blood cultures are positive for a potential pathogen, blood cultures must be repeated at each visit or more frequently if clinically indicated until negative cultures are obtained (see [Section 16.1.4.3](#) of the protocol).
- ^v Culture and Gram stain from an adequate quality sputum specimen or other respiratory specimen. At the EOT visit respiratory specimen cultures and Gram stains should be obtained only for subjects who are Clinical Failures and require alternative antibacterial treatment for CABP (see [Section 17.2.2.1](#) of the protocol).

